### **Serious Adverse Event (SAE)**

Number and percentage of patients with serious adverse events, regardless of study drug relationship, will be presented by primary system organ class and preferred term. Primary system organ classes will be sorted alphabetically and, within each primary system organ class, the preferred terms will be sorted in descending order of frequency.

If a patient reported more than one adverse event with the same preferred term, the adverse event will be counted only once. If a patient reported more than one adverse event within the same primary system organ class, the patient will be counted only once at the system organ class level.

All SAEs will be listed.

Adverse events and serious adverse events up to and including the Week 12 visit will be included in the database for the analysis at the primary analysis time point (Week 12).

#### **2.8.1.1 Adverse events of special interest / grouping of AEs**

Not applicable.

#### **2.8.2 Deaths**

Any death occurring between study day 1 and last day of treatment exposure + 30 days will be summarized by system organ class and preferred term for each treatment group and listed along with primary reason for death. Death occurring in the screening period and after 30 days of last dose of study treatment will be flagged.

### 2.8.3 Laboratory data

Descriptive summary statistics for the change from baseline to study visit will be presented by laboratory variable and treatment group. Change from baseline will only be summarized for subjects with both baseline and post-baseline values and will be calculated as:

$$\text{change from baseline} = \text{post-baseline value} - \text{baseline value}$$

For each variable, the maximum change (maximum decrease and maximum increase) from baseline, if appropriate for each study phase, will be analyzed analogously.

In addition, shift tables will be provided for all variables to compare a subject's baseline laboratory evaluation relative to the visit's observed value. For the shift tables, the reference laboratory ranges will be used to evaluate whether a particular laboratory test value was normal, low, or high for each visit value relative to whether or not the baseline value was normal, low, or high. If appropriate, the shifts to the most extreme laboratory test value within a treatment phase (either initial or entire) will be presented as well (including category "high and low"). These summaries will be presented by laboratory variable and treatment group.

The expanded laboratory ranges and the clinically notable abnormalities of key laboratory variables are given below:

**Table 2-2 Criteria for notable abnormalities**

---

#### Liver function and related variables

---

ALT (SGPT)	> 3 x Upper Limit of Normal (ULN)
AST (SGOT)	> 3 x ULN
Total bilirubin	> 1.5 x ULN
Alkaline phosphatase	> 1.5 x ULN

#### Renal function and electrolyte variables

Creatinine (serum)	> 1.5 x ULN
--------------------	-------------

#### Hematology values

Hemoglobin	≥ 2.0 g/dL decrease from baseline
Platelet count	< Lower Limit of Normal (LLN) White
blood cell	< 0.8 x LLN
Neutrophils	< 0.9 x LLN
Eosinophils	> 1.1 x ULN
Lymphocytes:	> 1.1 x ULN

---

## 2.8.4 Other safety data

### 2.8.4.1 ECG and cardiac imaging data

Not applicable.

### 2.8.4.2 Vital signs

Descriptive summary statistics for change from baseline for each post-baseline visit will be presented by vital signs, weight stratum, and treatment groups. Change from baseline will be calculated only for the subjects with both baseline and post-baseline values and will be calculated as:

Change from baseline = post-baseline value – baseline value

The number and the percentage of subjects with notable vital signs will be presented. The criteria for notable vital sign abnormalities are provided in Table 2-3 below:

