## **2 Statistical methods**

### **2.1 Data analysis general information**

Novartis Business Services will perform the statistical analysis.

Data will be analyzed by the statistical software SAS, Version 9.4 according to Section 9 (Data Analysis) of the study protocol which will also be available in Appendix 16.1.1 of the Clinical Study Report (CSR). Important information is given in the following sections and details are provided, as applicable, which will also be in Appendix 16.1.9 of the CSR.

At the Week 12 primary analysis time point, only the independent statistician and programmer(s) from Novartis will be unblinded in order to perform the interim analysis. The same SAP will be used for interim analysis.

It is planned that the data from all centers that participate in this protocol will be combined, so that an adequate number of subjects will be available for analysis.

Unless otherwise specified, all statistical tests will be conducted against a two-sided alternative hypothesis, employing a significance level of 0.05.

Efficacy, safety, and other data will be summarized as follows:

- for continuous variables, descriptive summary statistics (number of subjects, mean, standard deviation, median, 25th and 75th percentiles, interquartile range, minimum, and maximum) at each time point and for change from baseline to each visit will be reported by treatment group.

- for categorical variables, frequency and percentage will be presented at each time point by treatment group. Percentages will be calculated with respect to the number of subjects by treatment in the analysis set of interest.

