### **Other baseline characteristics**

In addition, the following variables collected at baseline will be summarized by treatment:

- height (in cm)
- weight (in kg)
- pulse (beats/min)
- blood pressure (mmHg)
- hematology
- clinical chemistry
- viral serology

- HIV 1/2
- Hepatitis B
- Hepatitis C
- serum pregnancy
- PASI score
- IGA mod 2011 score
- DLQI total score

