**Table 2-4 Rules for selecting values for analysis**

Timing of measurement	Type of data	Rule
Baseline	All data	The last measurement prior to first dose – note this may include measurements taken on the day of randomization (e.g. lab).
Post-baseline safety	Summary visit information (e.g. lab, ECG, vital etc.)	
The (non-missing) measurement closest to the target day will be used.
 
In the event two measurements are taken equally apart (e.g. 1 day before target date and 1 day after) the first one will be used.
 
If two measurements are taken on the same day then select the first one (using the time).
 
If two measurements are taken on the same date/time then use the first visit number (assuming this is the planned visit).
 
If two measurements are taken on the same date/time/CRF visit then use the average of two assessments

Post-baseline efficacy	All data except DLQI, EQ-5D and health assessment, PGIC	
The measurement closest to the target day will be used. In the event two measurements are taken equally apart (e.g., 1 day before target date and 1 day after), the earlier one will be used.
 
If two measurement are taken on the same day then select the first one using eCRF visit number.

Post-baseline safety	Summary visit information (e.g. laboratory values, vital signs, etc.)	
The (non-missing) measurement closest to the target day will be used. In the event two measurements are taken equally apart (e.g., 1 day before target date and 1 day after), the earlier one will be used.
 
If two measurements are taken on the same day then select the first one (using the time).
 
If two measurements are taken on the same date/time then use the first eCRF visit number (assuming this is the planned visit). If two measurements are taken on the same date/time/eCRF visit number then take the average value of these two results.

Post-baseline safety	Notable abnormalities (e.g.	The most extreme measurement in the window

---

Timing of measurement	Type of data	Rule
and efficacy	vital signs, PGIC) and CTCAE grading for laboratory values	will be used. Note this means a subject can have a notably high and notably low measurement within a window

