## **2.8 Safety analyses**

Analysis of safety data will be based on the Safety Set.

Any adverse event will be coded using the MedDRA dictionary for the Safety Set.

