**Table 2-3 Criteria for notable vital sign abnormalities**

Vital signs (unit)	Normal measure	Notable abnormality
Systolic blood pressure (mmHg)	90 to <120 mmHg	$\geq 140$ mmHg (hypertension) or $< 90$ mmHg (hypotension)
Diastolic blood pressure (mmHg)	60 to <80 mmHg	$\geq 90$ mmHg (hypertension) or $< 60$ mmHg (hypotension)
Pulse (bpm)	60 to 100(bpm)	$> 100$ bpm (tachycardia) or $< 60$ bpm (bradycardia)

Note: A blood pressure indicative of prehypertension (systolic blood pressure of 120 to <140 mmHg and/or diastolic blood pressure of 80 to <90 mmHg) will not be regarded as notable ([Chobanian, Bakris, and Black 2003](#)).

A listing of the newly-occurring notably abnormal vital sign will be provided.

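### The notable vital signs table in SAP 2.8.4.2 has no baseline condition, so it mixes persistent with new abnormality; new cases are listed but not counted by arm

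*SAP*

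**What the plan says.** SAP 2.8.4.2 plans two displays by arm. The first summarizes change from baseline at each post-baseline visit, by vital sign, weight stratum and treatment group. The second is the notable-value count: "The number and the percentage of subjects with notable vital signs will be presented". Table 2-3 defines notable by absolute limits: systolic at least 140 or below 90 mmHg, diastolic at least 90 or below 60 mmHg, pulse above 100 or below 60 bpm. Below that table the SAP adds: "A listing of the newly-occurring notably abnormal vital sign will be provided". It does not define newly-occurring.

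The denominator comes from SAP 2.1: "Percentages will be calculated with respect to the number of subjects by treatment in the analysis set of interest". SAP 2.8 names the set: "Analysis of safety data will be based on the Safety Set". For notable abnormalities, SAP Table 2-4 selects the post-baseline value used: "The most extreme measurement in the window". It also notes that one subject can be both notably high and notably low.

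For baseline, the SAP says that "the following variables collected at baseline will be summarized by treatment", and pulse and blood pressure are on that list. SAP 2.1 also says of categorical variables that "frequency and percentage will be presented at each time point by treatment group", which may yield a count of subjects notable at baseline. For laboratory data, SAP 2.8.3 says that "shift tables will be provided for all variables", comparing baseline with later values. No such table is stated for vital signs.

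**The concern.** The usual safety question about a threshold is how many subjects crossed it on treatment. The planned count does not isolate them, because subjects can enter already past it. The numeric limits in protocol exclusion 12 are systolic 180 mmHg or above and diastolic 95 mmHg or above. Systolic 140-179 and diastolic 90-94 therefore pass those limits while being notable under Table 2-3, and no low-pressure or pulse limit is stated. The exclusion is open-ended, so an investigator may still exclude such a subject on other grounds, but the numbers do not require it.

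Protocol Table 6-1 schedules vital signs at Weeks 4, 8 and 12 of the placebo-controlled period, so a subject notable at baseline has several chances to be counted. Vital signs are named in the safety objective. A reader looking for the new-onset rate by arm would find no stated table that reports it.

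**Working it through.** **Plan's own figure.** The documents state no rate for notable vital signs, so there is nothing to reproduce for this display. The only figure used is the arm size: 37 evaluable per arm / (1 - 0.10) = 41.1, rounded up to 42 randomized per arm, as in SAP section 3. I take 42 as the approximate Safety Set size per arm.

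**Formula.** For one criterion in one arm, let p0 be the share notable at baseline, q the share of those still notable after baseline, and s the new-onset rate among the rest.

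- Table percentage: T = p0 × q + (1 - p0) × s
- Arm difference at equal p0: (1 - p0) × (s1 - s0) + p0 × (q1 - q0)

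If q is equal in the arms the second term vanishes, and the table shows (1 - p0) times the new-onset difference.

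**Equal persistence.** Assumptions: s = 10% v 20% (difference 10 points, ratio 2.0), q = 1 in both arms. At p0 = 20%, T is 0.20 + 0.80 × 0.10 = 28% and 0.20 + 0.80 × 0.20 = 36%.

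| Assumed p0 | Table shows | Difference (points) | Ratio | At risk of 42 |
|---|---|---|---|---|
| 5% | 14.5% v 24% | 9.5 | 1.66 | 39.9 |
| 10% | 19% v 28% | 9 | 1.47 | 37.8 |
| 20% | 28% v 36% | 8 | 1.29 | 33.6 |
| 30% | 37% v 44% | 7 | 1.19 | 29.4 |

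The low rows are more plausible for high diastolic pressure, where the stated limit leaves only 90-94 mmHg.

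**Unequal persistence.** At p0 = 20% with the same onset rates:

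- q = 70% v 90%: 0.14 + 0.08 = 22% v 0.18 + 0.16 = 34%, a difference of 12 points.
- q = 90% v 70%: 0.18 + 0.08 = 26% v 0.14 + 0.16 = 30%, a difference of 4 points.

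The single count then merges two different treatment effects.

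**Chance baseline imbalance, no drug effect.** Assume s = 10% and q = 90% in both arms, with 12 of 42 v 6 of 42 notable at baseline.

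- Table: 12 × 0.9 + 30 × 0.1 = 13.8, or 32.9%, v 6 × 0.9 + 36 × 0.1 = 9.0, or 21.4%.
- New onset among those at risk: 3.0/30 = 10% v 3.6/36 = 10%.

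**The denominator has to change too.** At p0 = 20%, new cases over all subjects give 0.80 × 10% = 8% v 0.80 × 20% = 16%. That is again 8 points, not 10.

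**Precision.** With q = 1, the difference divided by its standard error at p0 of 5%, 10%, 20% and 30% is 1.11, 0.98, 0.79 and 0.66 for the all-subject count. For the at-risk rate it is 1.26, 1.23, 1.16 and 1.08. Neither separates the arms at this sample size.

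**The case against.** The strongest reply is that the plan is already adequate for a descriptive display.

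- **Weight.** Protocol 9.5.2 rests the safety assessment chiefly on adverse events and laboratory data and gives vital signs a supporting place. This stands, and it caps the importance of the point.
- **Change from baseline.** SAP 2.8.4.2 summarizes it by arm and visit, which is baseline-adjusted. This stands in part: it shows shifts in level and spread but does not count threshold crossings.
- **The listing.** With about 84 subjects, new cases can be counted by hand once treatment is known. This also stands in part. The information exists, but the reader must do the tally, find the at-risk denominator, and guess how newly-occurring was defined.
- **Adverse events.** Clinically significant values can be reported as adverse events, which are tabulated by arm. Protocol 6.5.2 leaves action to the investigator, however, so an asymptomatic crossing need not appear there.
- **The safety master analysis plan.** The SAP cites one that is not among the documents, and it may set a baseline condition. The point therefore concerns the SAP text only.

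A reader might infer from the laboratory shift tables that vital signs were held to a lower standard. The documents do not support that. Those tables use reference-range categories, not the notable criteria, and no subject count or new-onset listing is stated for notable laboratory values. The shift tables show only that a baseline-by-later display is already used in this SAP.

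**Conclusion.** The point holds as a minor matter of descriptive safety reporting. Read literally, the table combines persistent and new abnormality, and no stated table gives new onset by arm.

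With equal baseline prevalence and persistence, the difference in new onset is shrunk by the fraction p0. That is 5% to 30% over the assumed range, but p0, onset and persistence all lack a source in the documents, so the actual size is unknown. Chance imbalance at baseline in arms of about 42 can also create or hide a difference.

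A reader might infer that the table is biased for or against secukinumab. The documents do not support this: randomization balances baseline abnormality on average, and with equal persistence the effect is dilution. Nor is new onset concealed, since it is listed. No test is planned on this display and no efficacy result depends on it.

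**What to change.** In SAP 2.8.4.2 add, by treatment group, the number and percentage of subjects with newly-occurring notable values, in six separate rows: high and low systolic, high and low diastolic, high and low pulse. Direction matters because each row of Table 2-3 combines both. If a subject at 145 mmHg systolic at baseline were dropped from the whole row, a later fall to 85 mmHg would be missed.

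Define newly-occurring as notable in that direction after baseline but not at baseline. As a written exception to SAP 2.1, take as denominator the subjects not notable in that direction at baseline who have at least one post-baseline value.

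Present treatment period 1 as the secukinumab v placebo contrast. Present the entire treatment period descriptively only, with a note that placebo subjects switch to secukinumab at Week 12. Keep the all-subject count, the number notable at baseline and the listing, since persistence may itself differ between arms.

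The cost is SAP wording and extra columns in one table program. No new data are needed, and the listing already requires a newly-occurring flag. The table becomes slightly longer, and the new-onset denominator falls to about 40, 38, 34 or 29 of 42 per arm at assumed p0 of 5%, 10%, 20% or 30%, before removing anyone without a post-baseline value.

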**Table 2-3 Criteria for notable vital sign abnormalities**

Vital signs (unit)	Normal measure	Notable abnormality
Systolic blood pressure (mmHg)	90 to <120 mmHg	$\geq 140$ mmHg (hypertension) or $< 90$ mmHg (hypotension)
Diastolic blood pressure (mmHg)	60 to <80 mmHg	$\geq 90$ mmHg (hypertension) or $< 60$ mmHg (hypotension)
Pulse (bpm)	60 to 100(bpm)	$> 100$ bpm (tachycardia) or $< 60$ bpm (bradycardia)

Note: A blood pressure indicative of prehypertension (systolic blood pressure of 120 to <140 mmHg and/or diastolic blood pressure of 80 to <90 mmHg) will not be regarded as notable ([Chobanian, Bakris, and Black 2003](#)).

A listing of the newly-occurring notably abnormal vital sign will be provided.

## 2.9 Pharmacokinetic variables

Not applicable.

## 2.10 PD and PK/PD analyses

Not applicable.

## 2.11 Patient-reported outcomes

Not applicable for this section.

## 2.12 Biomarkers

The following cardiometabolic biomarkers will be analyzed individually:

[figure not shown]
- cardiometabolic function [lipid particle size, HDL function (cholesterol efflux)]
- measures of inflammation [TNF-Alpha, IL-6, C reactive protein, GlycA]

- adiposity [leptin and adiponectin]
- insulin resistance [insulin levels/glucose to yield HOMA-IR]

markers predictive of diabetes [apolipoprotein B, ferritin, IL-2 receptor A, IL-18, and fetuin-A]

The analysis method is given in section 2.7.2.1.

## 2.14 Interim analysis

The primary analysis at Week 12 will be considered as interim analysis. As Week 12 is the primary analysis time point, no adjustment to the significance level of 0.05 will be made.

## 3 Sample size calculation

The sample size was based on change from baseline in the target (arterial vascular uptake) to background (venous blood pool) ratio (TBR) from the aorta. Using a t-test, a clinically important mean treatment difference of 0.15, a (common) standard deviation (SD) of 0.196, an allocation ratio of 1:1, a two-sided significance level of 0.05, and a power of 0.90, it was determined that approximately 74 subjects (37 in each treatment group) are necessary (nQuery Advisor 7.0) (Bissonnette et al, 2013; Tawakol et al, 2013). Without adjusting for multiplicity, the sample size of 74 subjects will also provide at least 0.90 power for other biomarkers if the treatment difference is 0.76 SD or smaller. The general threshold for clinical importance is 1 SD. Allowing for a loss to follow-up rate of 0.10, approximately 84 subjects (42 in each treatment group) will be randomized.

## 4 Change to protocol specified analyses

Missing data will not be imputed using last-observation-carried-forward (LOCF) method for primary efficacy variable, since there is only one post-baseline visit.

For continuous secondary efficacy variables with more than one post-baseline assessment, missing data will be imputed using multiple imputation (in addition to LOCF).

For cardiometabolic biomarker, if the normality assumption is not tenable, additionally data will be analyzed using stratified Wilcoxon rank sum test.

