Fasting labs: plasma glucose	X																					
Viral serology lab analysis: HIV, Hepatitis B and C ^G	X																					X ^d
QuantiFERON [®] TB-Gold In-Tube test ^{G,H}	X																					X ^d
Serum pregnancy test ^{G,I}	X																					X ^d
Urine pregnancy test (local) ^J		X						X													X	X ^d
FDG-PET CT ^K		X ^L						X ^M													X	
Blood sample for cardio-metabolic biomarkers ^G		X [*]				X	X	X [*]						X			X				X [*]	
PASI	X	X				X	X	X				X		X		X		X		X	X	X ^d
IGA mod 2011	X	X				X	X	X				X		X		X		X		X	X	X ^d
Alcohol use assessment			X	X	X	X	X	X				X		X		X		X		X	X	X ^d
DLQI		X						X						X		X		X		X	X	

Period	SCR	Double-blind Treatment Period							Double-blind Induction Period			Open-label Treatment Period								Unscheduled Visit ^D		
		1	2	3	4	5	6	7	8 / EOT1 _{A,B}				9	10		11		12			13	14 / EOT2 _C
Visit	1	2	3	4	5	6	7	8 / EOT1 _{A,B}				9	10		11		12		13	14 / EOT2 _C		
Week	-4 to BL ^E	BL	1	2	3	4	8	12	13	14	15	16	20	24	28	32	36	40	44	48	52	
Visit window (Days)			±2	±2	±2	±2	±2	±2				±7		±7		±7		±7		±7	±7	
Assessment																						
AE/SAE assessment ^N	X	X	X	X	X	X	X	X				X		X		X		X		X	X	X
Randomization via IRT		X																				
Subject self-administration of study treatment at site		X	X	X	X	X	X	X				X		X		X		X		X		
Dispense study treatment to subject for at-home dosing								X				X		X		X		X				
Subject self-administration of study treatment at home and completion of Self-Administration Log ^O										X	X	X		X		X		X		X		
At-home Dosing Phone Reminder ^{F,P}										X			X		X		X		X			
Check Self-Administration Log and returned used/unused study treatment and packaging ^{F,Q}												X		X		X		X		X		X ^d

AE=adverse event; BL = Baseline; DLQI=Dermatology Life Quality Index; EOT1=End of Treatment 1; EOT2=End of Treatment 2; FDG-PET CT=18-fluorodeoxyglucose positron emission tomography with computer assisted tomography; HIV=human immunodeficiency virus; IGA=Investigator's Global Assessment; IRT=Interactive Response Technology; PASI=Psoriasis Area and Severity Index; SAE=Serious Adverse Event; SCR=Screening; TB=tuberculosis

* At Visits 2, 8, and 14, subjects are required to be fasting for a minimum of 8 hours prior to the blood sample collection for cardiometabolic biomarkers

Period	SCR	Double-blind Treatment Period							Double-blind Induction Period			Open-label Treatment Period								Unscheduled Visit ^D		
		1	2	3	4	5	6	7	8 / EOT1 A,B				9		10		11		12			13
Visit	1																					

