6.4.2 Cardiometabolic biomarkers

The following cardiometabolic biomarkers will be analyzed centrally at an analytical laboratory:

- Cardiometabolic function: lipid particle size, HDL function (cholesterol efflux);
- Inflammation: TNF-Alpha, IL-6, C-reactive protein, GlycA;
- Adiposity: leptin and adiponectin;
- Insulin resistance: insulin levels/glucose to yield HOMA-IR;
- Markers predictive of diabetes: apolipoprotein B, ferritin, IL-2 receptor A, IL-18, and fetuin-A.

Blood samples for cardiometabolic biomarkers will be collected at the scheduled time points as indicated in [Table 6-1](#).

Subjects will be required to fast for a minimum of 8 hours prior to the blood draw for the cardiometabolic biomarkers at the following visits only:

- Visit 2/Baseline
- Visit 8/Week 12
- Visit 14/Week 52.

A laboratory manual will be provided by the central laboratory with detailed information on biomarker sample collection, handling and shipment.

6.4.3 Assessment of total body surface area (BSA) and Psoriasis Area and Severity Index (PASI)

The Investigator or trained qualified designee will complete the PASI assessment at scheduled visits as indicated in [Table 6-1](#). Whenever possible, the same evaluator should perform this assessment at all study visits for a given subject. The Investigator is only responsible for collecting the components or scoring signs and total regional area. PASI calculations, including changes over time, will be done electronically, not by the Investigator.

The total BSA affected by plaque psoriasis will be estimated by the Investigator/trained qualified designee from the percentages of areas affected, including head, trunk, upper limbs and lower limbs (see below for full details of the PASI assessment). The following calculations will be done electronically: Each reported percentage will be multiplied by its respective body region corresponding factor (head=0.1, trunk=0.3, upper limbs=0.2, lower limbs=0.4). The resulting four percentages will be added up to estimate the total BSA affected by plaque psoriasis.

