9.5 Analysis of secondary variables

9.5.1 Efficacy variables

The secondary efficacy variables are the following:

- Change from baseline in each biomarker (see [Section 6.4](#))
- PASI 75 response (yes, no)
- PASI 90 response (yes, no)
- PASI 100 response (yes, no)
- IGA mod 2011 score of 0 or 1 (yes, no)
- Change from baseline in DLQI total score

Change from baseline in each biomarker and change from baseline in DLQI total score will be analyzed at each time point using the same ANCOVA model as for the primary efficacy variable, and missing data will be imputed using the LOCF method.

IGA mod 2011 score of 0 or 1 and PASI 75 / 90 / 100 responses will be analyzed at each time point using the Cochran-Mantel-Haenszel test to compare secukinumab and placebo, adjusting for body weight (<90 kg, ≥90 kg) ([Stokes, Davis, and Koch, 2012](#)). A 95% confidence interval for the difference between the two treatment groups in the proportion of subjects who are responders will be calculated using the normal approximation to the binomial distribution. For response (yes, no) at Week 12 (and other time points), a subject with a missing assessment will be considered as a responder (yes) if the subject meets the response criterion at the time of premature discontinuation from the study. Otherwise, the subject will be considered as a non-responder (no).

Analyses of the secondary efficacy variables will be based on the Full Analysis Set.

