Post-baseline efficacy	FDG –PET scan Cardiometabolic biomarker	Data will be analyzed as per CRF captured visit Data will be analyzed as per CRF captured visit but for discontinued patients only discontinued visit will be mapped to the next visit of the last available assessment before discontinuation within the same treatment period

---

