### **2.7.3 Handling of missing values/censoring/discontinuations**

For continuous secondary efficacy variables with more than one post-baseline assessment (i.e. cardiometabolic biomarkers and DLQI score), missing data will be imputed using the last-observation-carried-forward (LOCF) method. Baseline value will not be carried forward. If a subject has no post-baseline value, the missing value will not be imputed and the subject will be removed from the analysis.

For the subject who switch treatment after end of treatment period 1 (EOT 1), values of EOT1 are not carried forward to treatment period 2 (EOT 2).

For binary secondary efficacy variables (i.e. PASI 75,90,100 response and IGA mod 2011 0 or 1 response) at Week 12 (and other time points), a subject with a missing assessment will be considered as a responder (yes) if the subject meets the response criterion at the time of premature discontinuation from the study. Otherwise, the subject will be considered as a non-responder (no).

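### SAP 2.7.3 gives only LOCF for the biomarkers, which can carry draws with no fasting requirement into Week 12, while Section 4 adds multiple imputation with no model and no stated status

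*SAP*

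**What the plan says.** **Missing-data method.** SAP 2.7.3 rules that, for continuous secondary variables ("i.e. cardiometabolic biomarkers and DLQI score"), "missing data will be imputed using the last-observation-carried-forward (LOCF) method". Baseline is not carried forward, and "If a subject has no post-baseline value, the missing value will not be imputed and the subject will be removed from the analysis". Protocol 9.5.1 has the same method: "using the same ANCOVA model as for the primary efficacy variable, and missing data will be imputed using the LOCF method". SAP Section 4, which lists the departures from the protocol now in force, says that for these variables "missing data will be imputed using multiple imputation (in addition to LOCF"). Section 4 makes two other changes: no LOCF for the primary variable, and a van Elteren test for non-normal biomarkers. Both also appear in the body of the SAP (2.5.3 and 2.7.2.1). Multiple imputation does not, and SAP 5.4 gives no model for it.

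**Fasting.** Protocol 6.4.2 requires an 8-hour fast "prior to the blood draw for the cardiometabolic biomarkers at the following visits only": Baseline, Week 12 and Week 52. Table 6-1 marks those three draws with an asterisk ("At Visits 2, 8, and 14, subjects are required to be fasting for a minimum of 8 hours"). It leaves the Week 4 and Week 8 draws, and the draws between Week 12 and Week 52, unmarked.

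**Discontinued subjects.** Protocol 3.1.2 and footnote B of Table 6-1 ask subjects who stop in the double-blind treatment period to return for the Week 12/EOT1 assessments. For biomarkers, SAP Table 2-4 says that this "discontinued visit will be mapped to the next visit of the last available assessment before discontinuation within the same treatment period".

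**The concern.** There are two separate problems.

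First, a programmer working from 2.7.3 would not run multiple imputation at all, while one working from Section 4 would have to invent the imputation model, the number of imputations, the pooling and any combination with the van Elteren test. Nothing labels either result as main or sensitivity.

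Second, the stated LOCF rule can produce a value that is not comparable with its baseline. The protocol's own fasting requirement shows that fasting state was thought to matter, yet 2.7.3 makes no exception for insulin, glucose or the HOMA-IR derived from them. A carried value is also counted as if it had been measured at Week 12. At stake are the size and precision of the Week 12 biomarker differences, which are secondary results.

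**Working it through.** **1. The plan's own figures.** Inputs from SAP Section 3: difference 0.15, SD 0.196, two-sided alpha 0.05, power 0.90, loss 0.10. The standardized difference is 0.15/0.196 = 0.765. A two-sample t-test has power 0.901 with 37 per group and 0.893 with 36, so 37 per group (74) is reproduced. Then 37/(1 − 0.10) = 41.1, rounded up to 42 per group (84). This agrees with the plan.

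**2. How many subjects.** 0.10 × 42 = 4.2, so about 4 per arm could lack a Week 12 biomarker. This is an upper figure, as the next step shows.

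**3. Which value enters the Week 12 biomarker analysis.**
- Week 12 sample taken: observed, fasting required.
- Discontinued after the Week 8 draw, EOT1 attended: the EOT1 draw is mapped to Week 12. Fasting required, nothing imputed.
- Discontinued after the Week 4 draw, EOT1 attended: the EOT1 draw is mapped to Week 8, and LOCF carries it to Week 12. The carried value comes from a draw with a fasting requirement.
- Week 12/EOT1 sample missing, but a Week 4 or 8 draw exists: LOCF carries that draw, for which no fast was required, and the change is taken from a fasting baseline. **This is the faulty case.**
- No post-baseline value: removed.

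**4. Bias in the treatment difference (assumed shifts).** The documents do not give the effect of not fasting. Suppose it shifts a carried value by s SD, and that shares p_T and p_P of the two arms have such values. Each arm mean moves by p × s, so the difference moves by (p_T − p_P) × s.
- 10% in each arm: (0.10 − 0.10) × s = 0 for any s.
- 5% versus 15%: size 0.10 × s, which is 0.025, 0.05 or 0.10 SD for s = 0.25, 0.5 or 1.0.

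Type I error for the 5% versus 15% case uses arm variance 1 + p(1 − p)s², 42 per arm and 82 degrees of freedom. It is 0.052, 0.056 and 0.072 against the nominal 0.05. For s = 1.0 the variances are 1.0475 and 1.1275, the standard error is √(2.175/42) = 0.228, and the noncentrality is 0.10/0.228 = 0.44.

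**5. Understated uncertainty.** LOCF computes the standard error as if 42 values per arm were observed when about 38 were. If the carried values held no information about Week 12 and had the same spread as the observed ones, the reported standard error would be √(38/42) = 0.95 of the proper one, about 5% too small. To the extent that Week 4 or 8 values predict Week 12, the understatement is less.

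**6. DLQI.** Table 6-1 schedules no DLQI between Baseline and Week 12. A subject with neither a Week 12 nor an EOT1 questionnaire has nothing to carry: 2.7.3 removes that subject from the Week 12 analysis, while Section 4 might impute. The fasting point does not apply to DLQI.

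**The case against.** The strongest reply is that Section 4 adds to LOCF and does not replace it. Read with 2.7.3 and Protocol 9.5.1, it most naturally leaves LOCF as the main method and multiple imputation as supplementary. That stands. A reader might infer that the SAP sets up two rival p-values per biomarker, with the choice left until the data are seen. If either could be cited, the null chance of at least one p < 0.05 would be 0.059 to 0.070 per endpoint, for assumed correlations of 0.98 to 0.90 between the two statistics. The text does not set up that choice. What is missing is a label and a model.

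A reader might also infer that LOCF puts known non-fasting values into Week 12. The documents say only that fasting was not required at Weeks 4 and 8, and EOT1 draws do carry the requirement. The fault is therefore confined to subjects whose Week 12/EOT1 sample is missing. Nor do the documents support a large percentage distortion of HOMA-IR: they give no ratio of non-fasting to fasting values, and equal loss in the two arms leaves the difference unbiased.

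Finally, the SAP has no key secondary objective (2.6), and the biomarker power statement makes no multiplicity adjustment. This limits the consequence. It does not remove the fault, because the rule as written still gives a non-comparable value for three named measures.

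**Conclusion.** The point holds in a limited form. The SAP needs one stated main method for the continuous secondary variables, and its LOCF rule is unsuitable for insulin, glucose and HOMA-IR when the Week 12/EOT1 sample is missing. At the planned 10% loss this touches at most about 4 of 42 subjects per arm, and fewer if EOT1 is attended. Bias in the treatment difference arises only with unequal loss. It is 0.025 to 0.10 SD in the 5% versus 15% illustration, which rests on assumed shifts of 0.25 to 1.0 SD and on an assumed imbalance in loss. The understated standard error is a further small effect, for every biomarker with carried values. DLQI at Week 12 is affected only through removal versus possible imputation. The primary TBR analysis, which uses no LOCF, is untouched. The change is worth making because the plan already includes multiple imputation and needs no new data for it.

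**What to change.** In SAP 2.7.3:
- Make multiple imputation the main analysis for the biomarkers. State its model: treatment, body-weight stratum, baseline, and the Week 4 and Week 8 values as predictors, within treatment period 1. Give the number of imputations, the pooling rule, and how it combines with the van Elteren test.
- Keep LOCF as a labelled sensitivity analysis.
- For insulin, glucose and HOMA-IR, do not carry Week 4 or 8 values into the Week 12 analysis, nor values from other visits without a fasting requirement into Week 52. Use the fasting samples drawn at Week 12 or EOT1 and handle what remains missing by multiple imputation. Because Table 2-4 can relabel an EOT1 draw as an earlier visit, apply this rule by the visit at which the sample was drawn.
- For DLQI at Week 12, say whether a subject without a value is removed or imputed.

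Make Section 4 say the same. A repeated-measures model restricted to fasting draws would not be a substitute for these three markers: Week 12/EOT1 is the only post-baseline draw in period 1 with a fasting requirement, so the model would reduce to a single visit.

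The cost is SAP wording, a little more programming, and slightly wider intervals than under LOCF: up to about 5% (√(42/38) = 1.05) under the assumption in step 5 of the working.
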